11.12. Publication Policy

By signing the study protocol, the Investigator agrees with the use of results of the study for the purposes of national and international registration, publication and information for medical and pharmaceutical professionals. If necessary, Regulatory Authorities will be notified of the Investigator's name, address, qualifications and extent of involvement. The Investigator shall not publish any data (poster, abstract, paper, etc.) without having consulted with the Sponsor in advance and having received a written approval for such a publication. The sponsor-investigator will be responsible for publication of the data.

The sponsor-investigator must commit to publish and disseminate the study results in a timely manner without excessive restriction, regardless of whether the initial study hypothesis is confirmed or not.

11.13. Critical Documents

Before the Investigator starts the trial, the following documents must be provided to the site from the sponsor:

- 1. Regulatory approval (Health Canada NOL)(FDA in U.S. site) (CONEP in Brazil) (Meir Medical Centre Helsinki Committee in Israel);
- 2. Protocol, any substantial amendments;
- 3. Subject information/informed consent form;
- 4. Any other written information to be provided to the subject;
- 5. Subject recruitment procedures;
- 6. Templates for Delegation of Authority, CTSI form, Qualified Investigator Form and Health Canada REB Attestation where applicable.
- 7. Study procedures documents: SOPs/Operations Manual, eCRF system setup.
- 8. SAE reporting procedure for the study

These documents must be collected from site in order to begin recruitment and subject enrollment:

- Curricula vitae of Investigator and Sub-investigator(s) (current, dated and signed);
- 2. Favourable opinion from REB/IRB/IEC clearly identifying the documents reviewed;
- 3. Subject recruitment procedures that have not been identified by the protocol;
- 4. List of REB/IRB/IEC members and constitution;
- 5. Signed and dated agreement on the final protocol;
- 6. Signed and dated agreement on any substantial amendment(s), if applicable;
- 7. Copy of REB/IRB/IEC approved subject information/informed consent form;
- 8. Written information/advertisement;
- 9. Receipt of the Circular of Information/Notice d'accompagnement signed by Investigator (where applicable);
- 10. Laboratory certification and normal ranges;
- 11. Financial agreement(s).
- 12. Copy of completed Delegation of Authority

11.14. Clinical Study Report

Final clinical study reports will be prepared according to the ICH guideline on Structure and Contents of Clinical Study Reports. It will be prepared regardless of whether the study is completed or prematurely terminated. The Sponsor will provide each Investigator with a copy of the final report for retention.

12. STATISTICAL CONSIDERATIONS

12.1. Sample Size Considerations

Assuming a baseline risk of intubation or death by Day 30 of 30% in hospitalized patients with standard of care, a sample size of 1200 (800 in the CCP arm, and 400 in the standard of care arm) would provide 80% power to detect a relative risk reduction of 25% with CCP therapy using a 2-tailed test at level α = 0.05. This assumes no patient is lost to follow-up. Lost follow-up is expected to be minimal.

There is uncertainty about the intubation and mortality rate that will be observed in this study due to possibly evolving profile of COVID-19 patients admitted hospital over the course of the pandemic. To address this, a blinded sample-size re-estimation will take place when the primary outcome is available for 50% of the target sample. Sample size will only be adjusted if the estimated event rate is different than the originally specified event rate to a sufficient extent that the study is not expected to achieve the desired nominal power for the test of the primary outcome.

12.2. Planned Interim Analyses

A single interim analysis is planned when information on intubation or death at Day 30 is available for 50% of the target sample. An O'Brien-Fleming stopping rule will be employed.⁴⁴

The IDSMC may recommend early termination or modification of the protocol only when there is clear and substantial evidence of a treatment difference. More details about the interim analyses are described below as well as a separate guidance document for the IDSMC.

12.2.1. Safety Review

Safety analyses will evaluate serious AEs by treatment. The unblinded independent statistician will prepare these reports for review by the IDSMC. The IDSMC will review data on the occurrence of all reportable AEs at each of their meetings to ensure there are not significant numbers of unexpected AEs (AEs that do not fit with the known course of COVID-19, based on emerging data from the published and unpublished literature). If there is a significant number of unexpected AEs, the IDSMC will be asked to review unblinded safety data in an ad hoc meeting. Regular safety reports will be created to provide descriptive statistics on the occurrence of AEs to the IDSMC. The IDSMC may request safety data in a blinded or unblinded fashion as per their discretion.

12.2.2. Efficacy Review

A single interim analysis is planned when information on the primary outcome (composite of intubation or death at Day 30) are available for 50% of the target sample. The Lan-DeMets spending function⁵⁴ analog of the O'Brien-Fleming boundaries⁴⁴ will be used to monitor the primary endpoint as a guide for the DSMB for an overall two-sided type-I error rate of 0.05. Conditional power will be presented as an additional guide to the DSMB. Conditional power allows

computation of the probability of obtaining a statistically significant result by the end of the trial given the data accumulated thus far, incorporating a hypothesized treatment effect (e.g., the treatment effect assumed for sample size determination) thereafter. If conditional power is less than 20% under the original trial assumptions, consideration could be given to stopping the trial. An unblinded independent statistician will prepare the reports for IDSMC to review when making their recommendations. An IDSMC charter will further describe procedures and membership. An additional document on statistical methods related to the interim analyses will be provided to the IDSMC prior to their first meeting.

An additional document on statistical issues related to monitoring will be provided to the IDSMC prior to interim analyses.

12.3. Stopping Rules

If there are a concerning number of unexpected AEs, the IDSMC will be asked to review safety data in an ad hoc meeting. This study may be prematurely terminated if there is reasonable cause, including but not limited to: determination of unexpected, significant, or unacceptable risk to subjects; results of interim analysis; insufficient compliance to protocol requirements; data that are not sufficiently complete and/or not evaluable. If the study is prematurely terminated, the site Qualified Investigator will promptly inform study subjects and the REB as applicable. The site PI will assure appropriate follow-up for the subjects, as necessary. The sponsor will notify regulatory authorities as applicable. If there are a concerning number of unexpected AEs, the IDSMC will be asked to review all safety data in an ad hoc meeting.

This study may be prematurely terminated by the IDSMC and/or co-principal investigators and/or Sponsor if there is sufficient reasonable cause (see section 11.10)

12.4. Final Analysis Plan

The primary analysis will be based on the intention-to-treat population which will include data from all individuals who have been randomized. Outcomes will be attributed to the arm to which individuals were randomized irrespective of whether they received the planned intervention (e.g. plasma from a convalescent COVID-19 donor).

A per protocol analysis will also be performed. The per protocol sample will be comprised of eligible individuals who are randomized and are treated according to the protocol. In this trial, patients will be excluded from the per protocol analysis if any of the following protocol violations occur:

- -patient received less than two units of CCP
- -transfusion of second unit of CCP completed more than 24 hours after randomization (special consideration will be given for instances where 1 x 500 mL unit was given)
- -patient was randomized to SOC but received CCP

-patient was randomized despite being ineligible for the trial

12.4.1. Primary Efficacy Endpoint

Intubation or death at Day 30 is the primary endpoint.

Given the fact that the times from admission to discharge or death are expected to be relatively short, we are using a binary response indicating intubation or death at Day 30. The primary analysis will therefore be based on a 2-sided Wald test of the null hypothesis that probability of intubation or death is the same among individuals receiving CP or standard of care. The relative risk reduction for death (CCP versus standard of care) will be computed along with a 95% confidence interval.

Efforts to minimize loss-to-follow-up will be considerable and we are expected to have complete data on individuals for the primary outcome.

Sensitivity analyses will evaluate the impact of making different assumptions about missing data for secondary outcomes. These sensitivity analyses will be fully defined in the statistical analysis plan (SAP).

12.4.2. Secondary Endpoints

A cause-specific Cox regression model will be fitted for the intubation-free survival time defined as the first of the times of intubation or death with censoring at discharge or 30 days whichever comes first. A hazard ratio and 95% confidence interval will be computed from this fitted model.

Cumulative incidence functions will be estimated and plotted for each treatment arm for the time to intubation or death.

The restricted mean number of ventilator-free days over the first 30 days will be compared between the two groups based on a nonparametric tests.

The time to in-hospital death will be analyzed using a cause-specific Cox regression model treating the minimum of the time of discharge and 90 days as the censoring time. A hazard ratio and 95% confidence interval will be computed from this fitted model. Cumulative incidence functions will be estimated and plotted to estimate the proportion of patients who died during the initial hospitalization up to 90 days from randomization.

Finally, the survival status of individuals will be recorded at day 30 and the proportion of individuals who have died will be computed for each arm with a two-sample Wald test carried out based on the proportions.

Length of hospitalization over 90 days and length of stay in the ICU over 30 days will be modeled using a Cox regression without any distinction between reasons for discharge.

The proportion of patients needing ECMO over 30 days will be compared between the two arms based on a two-sided test of the difference between proportions.

The proportion of patients needing renal replacement therapy over the first 30 days will be compared between the two arms based on a Wald test.

The proportion of patients developing myocarditis over the first 30 days will be compared between the two arms based on a Wald test.

The change in EQ-5D-5L utility value from baseline will be compared between the two arms.

Incremental cost per quality-adjusted life year between the CCP and standard care over the 30-day time horizon.

No multiplicity adjustments will be implemented for the secondary analyses. Procedures for addressing missing data will be described in the SAP.

12.4.3. Safety Analysis

Safety endpoints include death through Day 30, SAEs, and severe AEs. These events will be analyzed univariately and as a composite endpoint. Time-to-event methods will be used for death and the composite endpoint. Each AE will be counted once for a given participant and graded by severity and relationship to COVID-19 or study intervention. AEs will be presented by system organ class, duration (in days), start and stop-date. AEs leading to premature discontinuation from the study intervention and serious treatment-emergent AEs should be presented either in a table or a listing. Counts of the number of individuals experiencing SAEs and severe AEs will be tabulated by event type and treatment group. They will then be tabulated by organ system, duration (in days), start and stop-date. Then the total number of events of each type will be summarized by group, allowing for each individual to contribute a count response for the number of AEs.

Each AE will also be characterized in terms of its relationship with COVID-19 or the current study intervention. The occurrence of transfusion associated AEs will likewise be compared between the two groups based on proportions.

Co-enrollment in other clinical trials is allowed in this protocol so we will record the nature of the interventions in these other trials and, if possible, the particular intervention to which our study participants were assigned.

Cox regression models will also be fitted for the time to the first of each SAE and severe AE to deal with the fact that death and discharge are censoring events.

AEs leading to premature discontinuation from the study intervention and serious treatmentemergent AEs will be tabulated or presented as a listing.

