4.2. Participant recruitment

Only hospitalized COVID-19 patients are eligible so recruitment efforts will be focused on identifying consecutive patients admitted to hospital with acute COVID-19 infection. No other external recruitment efforts are planned. At each participating hospital, a process for immediately identifying admitted patients with COVID-19 will be established. The mechanism of alerting the research assistants (RA) will be determined by local site principal investigator.

Patients who are confirmed to have COVID-19 infection and are admitted to hospital will be assessed for eligibility. Consent may be obtained verbally, given the infection control precautions

in place for these participants, as permitted by local research ethics committees. The RA (or a bedside physician if deemed acceptable by local research ethics boards [REB]) will obtain consent from the patient or legally authorized representative (LAR) by phone or videoconference. After consent is obtained, the RA will confirm eligibility remotely through a review of the electronic medical record and discussion with the bedside physician/nurse. Informed consent will be obtained remotely and may use a variety of visual aids (video brochure, a visual decision board). Documented written consent will be obtained from the patient or LAR as soon as possible as required by local REBs. At the time of assessing eligibility the RA will confirm with the site storing CCP that an ABO-compatible CCP plasma unit is available (for certain sites, group A plasma with low-titer anti-B (≤1:50) is allowed to be transfused to group B or AB patients). If 500 mL of CCP is available and eligibility criteria are met, the RA will randomize the patient. The RA will notify the blood bank of the allocation and a marker will be placed in the Laboratory Information System and the patient chart indicating that the patient is enrolled in the CONCOR-1 trial. For patients randomized to CCP, the RA will notify the bedside physician to order the study product. The CCP will be thawed in the blood bank, issued, and infused by the bedside nurse within 24 hours of randomization.

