9.4. Causality of Adverse Event

9.4.1. Relation to investigational product

The Investigator will assess the causality/relationship between the investigational product and the AE and record that assessment in the source documents and in the e-CRF. The most likely cause of an AE/SAE (for example disease under treatment, concomitant disease, concomitant medication, other) will be indicated in the e-CRF.

In the absence of a definite causal relationship, any adverse event that is considered to have a reasonable causal relationship with the investigational product should be classified as "probably related."

The causal relationship of the AE to investigational product will be described in terms of:

1. Related. The AE:

- 1. Follows a clear temporal sequence from administration of the investigational product.
- 2. Has no other possible explanations, such as the subject's clinical state, environmental or toxic factors or other therapies administrated to the subject.
- 3. Disappears or decreases on cessation or reduction in dose of the investigational product.
- 4. Follows a clear pattern of response to the investigational product.
- 5. Reappears or worsens upon re-challenge.

2. Probable. The AE:

- 1. Follows a reasonable temporal sequence from administration of the investigational product.
- 2. Could not be reasonably explained by the subject's clinical state, environmental or toxic factors or other therapies administrated to the subject.
- 3. Disappears or decreases on cessation or dose reduction of the investigational product.
- 4. Follows a known pattern of response to the investigational product.
- 5. Reappears or worsens upon re-challenge.

3. Possible. The AE:

- 1. Follows a reasonable temporal sequence from administration of the investigational product.
- 2. Could be reasonably explained by the subject's clinical state, environmental or toxic factors or other therapies administrated to the subject.
- 3. Follows a known pattern of response to the investigational product.

4. Unlikely. The AE:

- 1. Does not follow a reasonable temporal sequence from administration of the investigational product.
- 2. Could be reasonably explained by the subject's clinical state, environmental or toxic factors or other therapies administrated to the subject.
- 3. Does not follow a known pattern of response to the investigational product.
- 4. Does not reappear or worsen upon re-challenge.

5. Not related.

- The AE does not meet the above criteria.

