9.7. Type and Duration of Follow-up for Adverse Events

AE collection will begin at randomization and end at Day 30. Unresolved events at Day 30 will be marked as "ongoing at Day 30."

Adverse events will be monitored until Day 30. For participants still hospitalized at Day 30, hospital mortality will be followed up on Day 90.

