4.3.12. Incremental cost per quality-adjusted life year (QALY)

In addition to the cost of CCP, we will estimate the cost associated with the stay in ICU, hospitalization, use of ventilator and ECMO, diagnostics and procedures, and medications. The difference in cost between CCP and standard care will be divided by the difference in QALY calculated using the EQ-5D-5L to derive the incremental cost per QALY for CCP. 95% confidence interval for the incremental ratio will be assessed using a non-parametric bootstrapping with replacement approach with B=1000 times.

4.3.13. CPP transfusion-associated adverse events at Day 30

Adverse events judged to be definitely or probably related to CPP will be analyzed two ways: 1) using the Common Terminology Criteria for Adverse events (CTCAE; Grading 1-5)); and using the ISBT definitions for acute transfusions reactions (Grades 1-4). (Protocol section 4.3.13),

1. CTCAE Grading: The proportion of individuals experiencing CPP transfusion-associated adverse events (CTCAE Grades 1-5) will be reported overall by type, and severity. The total number of CPP transfusion-associated adverse

events will also be tabulated overall by type, and severity which will accommodate the possibilities of multiple adverse events per individual.

2. ISBT Grading: The proportion of individuals experiencing CPP transfusion-associated adverse events (ISBT Grades 1-4) will be reported overall by type, and severity. The total number of CPP transfusion-associated adverse events will also be tabulated overall by type, and severity which will accommodate the possibilities of multiple adverse events per individual.

4.3.12. Grade 3, 4, and 5 adverse events at Day 30

See protocol section 9 for additional details regarding AE definitions.

The proportion of individuals experiencing Grade 3, 4 or 5 (as per CTCAE criteria) adverse events will be analyzed overall and by treatment arm by type, severity grade, and expected/unexpectedness. The total number of Grade 3, 4 or 5 adverse events will also be tabulated overall and by treatment arm by type, severity grade and expected/unexpected which will accommodate the possibilities of multiple events per individual.

4.3.13. Grade 3, 4 and 5 serious adverse events at Day 30

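### Plasma is given once, within 24 hours of randomization, but Grade 3 or higher adverse events are compared between arms only to Day 30, so an acute excess can be diluted

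*Protocol*

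**What the plan says.** **Exposure.** The plasma is to be "infused by the bedside nurse within 24 hours of randomization" (Protocol 4.2). Protocol 5.7 sets the same limit for the complete dose. Protocol 1.5 lists allergic and febrile reactions, TRALI, TACO and hemolysis among the transfusion risks.

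**Follow-up.** "AE collection will begin at randomization and end at Day 30" (Protocol 9.7). Onset date is recorded for each event (Protocol 9.6).

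**Between-arm safety analyses.**
- Protocol 12.4.3 analyses death, SAEs and severe AEs singly and as a composite, with time-to-event methods for death and the composite. It tabulates patients and events by type and arm, and adds that "Cox regression models will also be fitted for the time to the first of each SAE and severe AE".
- The SAP section on Grade 3, 4 and 5 adverse events (the second section numbered 4.3.12) gives proportions and totals at Day 30 by arm, type, grade and expectedness.
- The SAP section on serious adverse events (the second 4.3.13) gives a relative risk reduction with a 95% interval and a cumulative incidence plot by arm. It limits SAEs to unexpected events that need expedited reporting, plus TRALI and TACO.

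**Attributed reactions.** "Adverse events judged to be definitely or probably related to CPP will be analyzed two ways" (SAP section on transfusion-associated events, the first 4.3.13), with results reported overall. Protocol 12.4.3 instead says these events are compared between the groups.

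Neither document sets an early window, a time-varying hazard ratio or a check of proportional hazards for these analyses.

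**The concern.** After a single infusion, direct harm is concentrated in the first day or two, while severe COVID-19 events accumulate over weeks. A constant hazard ratio is not plausible for that pattern. A 30-day proportion or hazard ratio mixes a short period in which CCP may add events with a long one in which it adds none or prevents some.

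The attributed-reaction analysis covers this only in part. Protocol 9.4.1 defines both of its top two causality categories by the absence of an alternative explanation in the patient's "clinical state, environmental or toxic factors or other therapies administrated to the subject". Respiratory worsening in a COVID-19 patient on oxygen often has such an explanation, and the judgement is made open-label. Events attributed to COVID-19 then appear only in the all-cause tables, where the window is 30 days. At stake is a safety conclusion of no difference, or of fewer severe events with CCP, when there was an excess around the transfusion.

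**Working it through.** **1. The plan's own figure.** Protocol 12.1 assumes 30% v 22.5% (25% relative reduction), two-sided 0.05, 80% power and 2:1 allocation. The pooled rate is (30 + 2 × 22.5)/3 = 25%.

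n(SOC) = [1.96√(0.25 × 0.75 × 1.5) + 0.8416√(0.30 × 0.70 + 0.225 × 0.775/2)]² / 0.075² = 399.1, taken as 400, total 1200. Power at that size is 80.1%, so the figure reproduces. No power or precision is stated for safety.

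**2. Assumed inputs (not in the documents).** Background Grade 3 or higher events by Day 30: 30-45%, with 10% as a low case. The lower end of the main range borrows the 30% assumed for intubation or death. Acute CCP excess: 3-5 points, within 48 hours. Later hazard ratio: 1.0, or 0.75 borrowed from the design effect. Constant background hazard; no censoring at discharge.

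**3. One case by hand: 30% background, 4-point excess, no later effect, Day 3 taken as 72 hours.**
- λ = −ln(0.70)/30 = 0.01189 per day.
- Day 3: SOC 1 − e^(−3λ) = 3.50%; CCP 1 − 0.96 × 0.9650 = 7.36%; difference 3.86 points.
- Standard errors: pooled √(0.0607 × 0.9393 × (1/800 + 1/400)) = 0.0146; unpooled 0.0130. Power = Φ[(0.0386 − 1.96 × 0.0146)/0.0130] ≈ 78%.
- Day 30: SOC 30.0%; CCP 1 − 0.96 × 0.70 = 32.8%; difference 2.8 points; both standard errors about 0.028. Power ≈ Φ[(0.028 − 0.0559)/0.0283] = 16%.

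With the hazard 25% lower after 48 hours, CCP at Day 30 is 1 − 0.96 × e^(−23λ) = 27.0%, a risk ratio of 0.90. At Day 3 it is still 1 − 0.96 × e^(−2.75λ) = 7.1% v 3.5%.

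**4. Simulation, 800 v 400, chance of a significant harm signal.**

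| Background by Day 30 | Later effect | Mean 30-day HR | 30-day Cox | Proportion at Day 3 |
|---|---|---|---|---|
| 30-45% | none | 1.07-1.17 | 10-28% | 44-92% |
| 30-45% | 25% reduction | 0.84-0.94 | below 1% | 30-87% |
| 10% | none | not tabulated | 27-65% | 89-99.8% |

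The result depends somewhat on where Day 3 ends. Randomization is Day 1 (SAP 2.1), so the end of Day 3 falls 48-72 hours later. For the weakest case with no later effect (45% background, 3 points), a full 72 hours gives 8.63% v 5.80%, and the formula in step 3 gives about 40% instead of 44%.

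**5. Wider grid.** A second simulation placed the excess in the first 24 hours and tested at 24 hours, which favours the early window. Over 5-50% background, 2-6 points excess and later hazard ratios of 1.0, 0.9 and 0.75, the mean 30-day hazard ratio ran from 0.79 to 2.29. With no later effect it stayed above 1 (1.04 to 2.29). At 5% background and 6 points the 30-day Cox model already detected harm in 93% of trials.

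**The case against.** The planned safety analysis has more in it than the Cox models, and several stronger readings fail.

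- A reader might infer that a single Cox hazard ratio is the only safety comparison. It is not. Protocol 12.4.3 adds these models to counts and proportions by arm, and tables use start and stop dates. The SAP plans no Cox model for adverse events.
- A reader might infer that SAEs too are swamped by COVID-19 events. Protocol 9.2 excludes natural-history events and study outcomes from SAEs, and the SAP narrows them further. Its SAE cumulative incidence plot would show early separation. The dilution argument applies to Grade 3 or higher AEs and to the pooled composite.
- A reader might infer that respiratory worsening can never count as related. Protocol 9.4.1 also says that an event with a reasonable causal relationship should be called probably related. TRALI and TACO are reported regardless of seriousness (Protocol 9.9) and enter the SAP's SAE analysis.
- A reader might infer that the hazard ratio will be below 1. That needs a later benefit.

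Event-type tables also dilute less. For a distinctive reaction with an assumed 0.5-2% background, a 3-point excess would be detected over the full 30 days with about 73-94% power. SAP 4.3.1 plots intubation or death over time, and the IDSMC sees unblinded tabulations monthly (SAP 4.5 and 4.11).

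All of this stands, and it narrows the point. None of it provides a prespecified, attribution-free comparison of severe events near the infusion. The plots are descriptive and cover SAEs or the efficacy composite. Attributed reactions depend on open-label judgement and have no comparator in the SAP. Type tables help least when the acute event looks like COVID-19.

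**Conclusion.** The point holds in limited form. Every prespecified by-arm comparison of Grade 3 or higher AEs, and of the pooled safety composite, covers the whole period to Day 30, so an acute excess can be diluted. It can be reversed in sign only if CCP also lowers later events.

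The loss is large when background events are common and shrinks as they become rarer; the table in the working gives the size. Background rate, excess and later effect are all assumptions. The documents support the absence of an early comparison, but not a prediction that harm will be hidden. This is an inexpensive improvement to the plan, worth making before arm-level safety data are analysed.

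**What to change.** In Protocol 12.4.3 and the SAP section on Grade 3-5 adverse events:

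1. Add a comparison by arm, regardless of attribution, of patients with any Grade 3 or higher AE with onset from randomization to the end of Day 3. Use the same time origin in both arms and report the risk difference with a score or exact 95% interval.
2. Report intubation or death in the same window separately. An all-cause count removes attribution bias but not the closer observation that CCP patients receive during infusion, and this endpoint is less open to it.
3. Report Day 4-30 events separately.
4. Split the Cox model for the safety composite and severe AEs at the end of Day 3.

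Onset dates and daily ventilation status are already collected (Protocol 9.6 and 8.5), so no new data are needed. A window shorter than a day would need onset times. The cost is SAP wording, one table and one additional safety comparison.
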